#### **Statistical Analysis Plan**

## 1. Statistical aspects of the clinical trial design

Intention-to-treat analyses will be used to test intervention efficacy.

## 2. Process of data selection for analyses

Data were selected for analysis in order to address study aims focused on evaluating the intervention in terms of primary and secondary outcomes as well as determining mediating mechanisms of change as well as moderators. (Due to premature study termination, only analyses with respect to primary and secondary outcomes will be conducted.)

## 3. Detailed analyses of data items

Descriptive statistics will be performed on all study variables. We will transform any outcomes with skewed distributions (log or other as appropriate) to stabilize error variances and reduce the influence of outliers in regression models. To address potential bias from differential randomization and dropout, we will use covariates and non-response weights. Socio-demographic characteristics that significantly differ by intervention condition at will be included as covariates. Nonresponse weights will be used to address any potential differences between participants with complete data for at least one follow-up wave versus participants with only baseline data. Weights will be created using the inverse of the estimated probability of completing any follow-up survey, based on a multivariable logistic regression using socio-demographic and psychosocial variables that were not missing for any participant.

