## 4. Procedures and methods employed for analyzing the data

Analysis Plan. To test intervention effects under the Study Aim, we will use intention-to-treat analyses comparing intervention to control group outcomes. For inadequate healthcare engagement (<1 ambulatory visit, ≥1 emergency department visit, or ≥1 hospitalization in past 6 months) and receipt of evidence-based preventive care, we will conduct logistic regressions predicting whether participants had inadequate health care utilization or received evidence-based care within the entire follow-up period (yes/no). For coping, we will analyze all follow-up responses with repeated-measures linear regressions that include fixed effects for intervention condition, baseline value of the outcome, and covariates, employing a sandwich estimator to account for within-participant clustering; each participant can contribute up to three follow-up responses (from the 4-, 8-, or 12-month surveys).

Statistical Power. Based on our prior research, we anticipate medium effect sizes (0.5 SD). For analyses comparing intervention vs. control on continuous outcomes (e.g., coping) at follow-up, with a very conservative estimate of 240 participants (120 per group), there will be 80% power to

detect a difference of .36 SD (a small-to-medium effect size). For receipt of evidence-based preventive care, we used percentages from an analysis of our preliminary data, in which receipt of evidence-based care for CVD prevention and treatment ranged from 5.1% to 58.4% (and was lower for people living with HIV vs. people who were HIV-negative) [Ladapo JA, Richards AK, DeWitt CM, Harawa NT, Shoptaw S, Cunningham WE, Mafi JN. Disparities in the quality of cardiovascular care between HIV-infected versus HIV-uninfected adults in the United States: a cross-sectional study. J Am Heart Assoc. 2017;6(11):e007107. PubMed PMID: 29138182; PMCID: 5721786]. Thus, we estimated 80% power at 12-month follow-up to detect minimum between-groups difference representing small-to-medium effect sizes:

Control Group %	Minimum Detectable Difference	Effect Size (Cohn's D)
5%	11.0%	.37
30%	17.6%	.36
60%	16.8%	.36

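### Socio-demographic covariates enter the models only when a significance test finds an arm difference, which forgoes most of the power that pre-specified adjustment would give the two primary logistic analyses

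*Combined protocol and SAP*

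**What the plan says.** SAP section 3 introduces adjustment as a bias control: "To address potential bias from differential randomization and dropout, we will use covariates and non-response weights". The rule that follows is "Socio-demographic characteristics that significantly differ by intervention condition at will be included as covariates". It lists no variables and sets no test level. The word giving the timepoint is absent after the preposition; baseline is the natural reading.

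SAP section 4 describes the primary analyses as follows: "we will conduct logistic regressions predicting whether participants had inadequate health care utilization or received evidence-based care within the entire follow-up period (yes/no". No fixed covariate and no baseline outcome value is named there, so section 3 is the only stated route for a covariate into these two models. The secondary coping model differs. It has "fixed effects for intervention condition, baseline value of the outcome, and covariates", so baseline coping is always included.

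The power paragraph in SAP section 4 works "with a very conservative estimate of 240 participants (120 per group") and makes no allowance for covariates. The non-response weights in SAP section 3 also use socio-demographic and psychosocial variables, but they model completion of any follow-up survey. They do not adjust the arm comparison for prognosis.

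**The concern.** Allocation is random (protocol section 2), so baseline differences between arms are chance. A p-value for such a difference does not say whether the characteristic is worth adjusting for; that depends on how strongly it predicts the outcome. A rule triggered by the p-value admits irrelevant characteristics that happen to differ and leaves out strong predictors whose imbalance falls short of significance.

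Two things are at stake. The first is power: adjusting for strong predictors raises it, and this rule almost never does so. The second is pre-specification: the primary models cannot be written down until the arms have been compared on a set of variables, at a test level, that the plan does not state.

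**Working it through.** **Inputs from the documents.** 370 enrolled, about 185 per arm (protocol sections 2 and 4). For power: 120 per arm, 80% power, 0.36 SD for continuous outcomes, and differences of 11.0, 17.6 and 16.8 points at control rates of 5%, 30% and 60% (SAP section 4).

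**Assumptions.** Two-sided alpha of 0.05, which is not stated but reproduces the plan's figures; a one-sided 0.05 would give 0.32 SD. Prognostic strength is not given either, so a range is used.

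**1. The plan's own figures.**
- Continuous: detectable difference = (1.96 + 0.842) × √(2/120) = 0.362 SD. Power at 0.36 SD is 79.6%.
- Binary: power = Φ{[Δ − 1.96√(2p̄(1−p̄)/n)] / √[(p₁(1−p₁)+p₂(1−p₂))/n]}. For 30% against 47.6%, p̄ = 0.388 and n = 120: (0.176 − 1.96 × 0.0629)/0.0619 = 0.85, so power is 80.3%.
- The 5% and 60% rows give 79.8% and 80.3%.

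The stated figures reproduce without any covariate adjustment.

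**2. How often the rule acts.** At 120 per arm a characteristic is selected only if the arms differ by more than 1.96 × √(2/120) = 0.25 SD, or, for a 50% binary factor, 1.96 × √(2 × 0.25/120) = 12.7 percentage points. This happens in about 5% of trials for any one characteristic. If 10 independent ones were tested (an assumed number), at least one would enter in 1 − 0.95¹⁰ = 40% of trials, without regard to prognosis.

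**3. Power for the primary logistic models.** Simulation with 4,000 trials per scenario, 120 per arm and one standard normal covariate, with the marginal rates held at the plan's values:

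| Covariate log OR per SD | 30% vs 47.6%: rule | 30% vs 47.6%: always adjusted | 60% vs 76.8%: rule | 60% vs 76.8%: always adjusted |
|---|---|---|---|---|
| 0.5 | 80.7% | 82.1% | 80.8% | 82.4% |
| 1.0 | 80.9% | 86.6% | 81.1% | 86.6% |
| 1.5 | 82.4% | 91.4% | 82.2% | 91.4% |

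A separate run of the 30% case gave 81.3/81.3/81.1% under the rule and 83.1/86.0/90.5% always adjusted. With no adjustment, power in the 30% case was 80.7/80.1/81.2%, so the rule recovers about 0 to 1 point.

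**4. Where the logistic gain comes from.** At log OR 1.0 (30% case), adjustment raises the standard error of the treatment log odds ratio from 0.272 to 0.303, but the log odds ratio itself rises from 0.751 (marginal) to 0.902 (conditional). The ratio goes from 0.751/0.272 = 2.76 to 0.902/0.303 = 2.98. The gain is in power; the interval on the log odds ratio does not narrow.

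**5. Continuous outcome.** Power at 0.36 SD = Φ(0.36/√(2(1−R²)/120) − 1.96): 79.6% at R² = 0 and 83.6/87.7/91.5% at R² = 0.1/0.2/0.3. For coping, R² here means variance explained beyond baseline coping.

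**6. Type I error under the rule.** 4.4% to 5.4% in the logistic scenarios and 4.2% to 5.1% in the linear ones.

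**The case against.** **The plan is powered without adjustment, and its design case is cautious.** This is correct. The detectable differences reproduce with no covariates, so a reader who infers that the power claim fails would be wrong. SAP section 4 also anticipates 0.5 SD, and 370 are enrolled. For a continuous outcome, unadjusted power is 97% at 120 per arm and 0.5 SD, and 93% at 185 per arm and 0.36 SD. Adjustment at R² = 0.2 then adds only about 2 to 4 points.

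**The rule guards against bias.** A reader might go the other way and infer that omitting covariates biases the trial or inflates false positives. One adverse draw can be made to look that way. With a covariate correlated 0.4 with the outcome and imbalanced at z = 1.5, the false-benefit risk is 1 − Φ((1.96 − 0.6)/√0.84) = 6.9%. With the imbalance reversed it is 0.3%, and averaged over all non-selected imbalances it is about 2.3%, against a nominal 2.5%. There is no overall inflation. Nor does the rule choose covariates by their effect on the treatment result, since it tests them against arm and not against outcome. Still, as a safeguard the rule is weak, because it ignores a z = 1.5 imbalance in a strong predictor.

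**Baseline is already adjusted for.** True of coping, so it would be too broad to say that all models lose the benefit of the baseline survey. SAP section 6 speaks of comparing change in primary as well as secondary outcomes, but it gives no model term, and the logistic description in section 4 has none.

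**The size is assumed.** This stands. The documents give no prognostic strength, no number of characteristics and no test level. For a weak covariate the loss is only about 1.5 points.

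**Conclusion.** The point holds as a matter of efficiency and pre-specification. The trigger is unrelated to prognostic value, so the rule leaves the primary logistic models close to unadjusted and undefined until the arms have been compared. At the plan's design case, the power forgone runs from about 1.5 points for a weak covariate to about 9 for a very strong one (about 81% against 82% to 91%), and less with better retention or a larger effect. For coping, only the gain from socio-demographics beyond baseline coping is lost. The documents do not support reading this as a validity failure. Confidence is high on the mechanism and lower on the size, which depends on assumed prognostic strength and a two-sided 5% level.

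**What to change.** Replace the significance-test sentence in SAP section 3, which also removes the incomplete timepoint. Before the arms are compared:

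- Fix a short list of prognostic baseline covariates from those the survey already collects. The documents do not list the socio-demographic items, so the sponsor must choose from its own instrument.
- Add the baseline value of each primary outcome where it was measured.
- Include the list in every primary and secondary model, whatever the observed balance.
- Keep it to a few parameters if an outcome is rare. In the plan's 5% row, 120 × 0.05 + 120 × 0.16 is only about 25 events.
- Present baseline tables without tests.

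SAP section 2 describes the primary and secondary analyses as still to be done, so the change can be made now. If the arms have already been compared, disclose this and date the choice of list.

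The cost is a short text change and a few degrees of freedom, with no new data if the list is drawn from what was collected. The logistic odds ratio becomes conditional on the covariates, and the report should say so.

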#### 2. How it will be done

A total of 370 Black participants will be recruited; approximately half will be randomly assigned to receive the coping intervention and half to a no-treatment control condition. There will be about 10 cohorts of about 15 participants each for both intervention and control. Participants will be randomized to an intervention or control group after they complete the baseline survey. Participants will complete four surveys, starting with the baseline survey, and followed by 4-, 8-, and 12-month post-baseline follow-up surveys to assess health care engagement and receipt of evidence-based preventive care (e.g., cancer and diabetes screening, cardiovascular disease prevention, immunization, HIV prevention), and other topics such as coping strategies.

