#### 8. What information will be collected

- 1. From baseline to 12-month post-baseline we will assess the Primary Outcome Measure: Proportion of Participants Who Have Inadequate Healthcare Utilization (self-reported). The survey will assess number of medical care visits in different settings (usual source of medical care, primary care visits, missed visits, urgent care, emergency department, hospital inpatient, residential care facility, hospital outpatient clinic, other type of clinic, dental care provider, home healthcare). We will construct measures of inadequate service utilization as having: (1) fewer than 1 ambulatory visit, (2) at least 1 emergency department visit (without subsequent hospitalization), or (3) at least 1 hospitalization in the past 6 months. Higher numbers of hospital visits and emergency department use likely results from not receiving indicated outpatient treatment, which can prevent complications, even among those who experience multiple chronic conditions.
- 2. From baseline to 12-month post-baseline we will assess the Primary Outcome Measure: Proportion of Participants Receiving Evidence-based Care Across Conditions and Assessments (self-reported). We will calculate receipt of evidence-based care as receipt of all eligible services within health condition categories (cancer screening, CVD prevention, immunization, diabetes care, HIV prevention, HIV treatment), and create an "all-or-none" measure across all categories.
- 3. From baseline to 4 months, to 8 months, and to 12 months, we will measure change the Secondary Outcome Measure, Adaptive Coping Strategies (Social Support Seeking; e.g., "I get emotional support from others"). Relevant items on the Brief Cope a general measure of coping strategies, will be adapted to assess frequency of use of each strategy, using the instructions, "indicate the extent you do what the item says when you are faced with discrimination," and response options 1 = "I haven't been doing this at all," 2 = "I've been doing this a little bit," 3 = "I've been doing this a medium amount" and 4 = "I've been doing this a lot."

Note: The study team originally planned to validate self-reported health care behaviors and outcomes with medical records data, but the grant was terminated before the team could collect these objective data.

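### Utilization is scored as one yes/no over up to three surveys, but the weights correct only for having no follow-up survey, so unequal survey completion by arm can create a false difference

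*Combined protocol and SAP*

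**What the plan says.** Protocol section 2 has a baseline survey "followed by 4-, 8-, and 12-month post-baseline follow-up surveys". Protocol section 8 builds inadequate utilization from three components (no ambulatory visit, an emergency department visit, a hospital stay), the last worded "at least 1 hospitalization in the past 6 months". I read the 6-month recall as applying to all three; Protocol section 1 attaches the same window to ambulatory visits.

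SAP section 4 fits a logistic regression to each primary outcome, scored "within the entire follow-up period (yes/no"). For coping it instead models the individual responses: "each participant can contribute up to three follow-up responses (from the 4-, 8-, or 12-month surveys").

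Missing follow-up is handled in SAP section 3 by weights that contrast "participants with complete data for at least one follow-up wave versus participants with only baseline data". They are defined as follows: "Weights will be created using the inverse of the estimated probability of completing any follow-up survey". The weight model uses fully observed demographic and psychosocial variables; trial arm is not named among them.

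Neither document says how the yes/no is formed for a man with one or two of the three surveys. SAP section 6 mentions comparisons at single timepoints and longitudinal models, but adds no rule for missed surveys.

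**The concern.** An ever/never outcome depends on how long one looks. A man who returns one survey has fewer chances to be flagged than a man who returns three, yet the planned weight treats both as followed. SAP section 3 presents covariates and weights as protection against bias from dropout that differs by arm, but this weight does not see partial follow-up.

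One arm is asked to attend eight group sessions and the other receives nothing, so unequal survey completion is a realistic risk, though the documents do not report it. If it occurs, the utilization comparison is shifted with no treatment effect present. The direction depends on a scoring rule the SAP does not give. If one flagged survey is enough, the arm with fewer surveys looks better on inadequate utilization. If a component must be reported on every completed survey, that arm looks worse.

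Coping is not exposed, because each response is modelled separately. Evidence-based care is uncertain: Protocol section 8 defines it ("We will calculate receipt of evidence-based care as receipt of all eligible services within health condition categories") without a recall window, and exposure would be smaller if the month-12 survey covers the whole year.

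**Working it through.** **1. The plan's own power figures (SAP section 4).** With 120 per group, two-sided 5% (assumed; the SAP states no alpha) and normal approximations, power is 79.6% for 0.36 SD, 79.8% for 5% vs 16.0%, 80.3% for 30% vs 47.6% and 80.3% for 60% vs 76.8%. The stated 80% is reproduced. I use 120 per arm below.

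**2. Months observed.** This needs no assumption beyond the stated recall. A survey at month m covers months m-5 to m; take the union and keep months 1 to 12.

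| Surveys completed | Post-baseline months covered | Count |
|---|---|---|
| 4 only | 1-4 (two recalled months precede baseline) | 4 |
| 8 only | 3-8 | 6 |
| 12 only | 7-12 | 6 |
| 4 and 8 | 1-8 | 8 |
| 4 and 12 | 1-4, 7-12 | 10 |
| 8 and 12 | 3-12 | 10 |
| All three | 1-12 | 12 |

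**3. False difference when any flagged survey counts.** Assumptions: no true effect; correlated yes/no reports from a latent normal (correlation 0.3 or 0.6); shares with 3/2/1 surveys of .80/.13/.07 in one arm and .70/.20/.10, .60/.25/.15 or .50/.30/.20 in the other.

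Simulated probability of ever being flagged with 1/2/3 surveys:
- per-survey rate 0.3: 30% / 43-47% / 50-58%
- per-survey rate 0.4: 40% / 54-59% / 62-70%

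Arm rate = sum over k of (share with k surveys) × (ever-rate with k surveys). Example at rate 0.4, correlation 0.3, from rounded inputs:
- lower-completion arm: .50×70 + .30×59 + .20×40 = 60.7%
- other arm: .80×70 + .13×59 + .07×40 = 66.5%
- false difference: 5.8 points
- standard error: √[(.607×.393 + .665×.335)/120] = 0.062, a shift of 0.93 standard errors
- two-sided rejection: P(Z > 1.03) + P(Z < -2.89), about 15%

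Full ranges, including the alternative scoring in step 4:

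| Completing all three | Any flagged survey, rate 0.3-0.4 | Type I error | Composite, no-visit over whole period | Type I error, at most |
|---|---|---|---|---|
| 70% vs 80% | 1.1-1.7 points | 5.4-5.9% | -0.5 to 1.1 points | 5.3% |
| 60% vs 80% | 2.5-3.8 | 6.8-9.4% | -1.2 to 2.3 | 6.5% |
| 50% vs 80% | 3.9-5.9 | 9.3-15.6% | -1.9 to 3.5 | 8.4% |

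**4. Composite.** No-visit rate 0.2-0.4 and emergency/hospital rate 0.1-0.3, taken as independent. Absence of a visit counts only if every completed survey reports it; an emergency or hospital event counts if any survey does. The two partly cancel, so the sign is not fixed. Judging every component per survey with the same rates gives 1.2-1.8, 2.7-4.0 and 4.2-6.1 points.

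**5. Rate 0.05**, possible for an all-or-none care measure: 0.4-0.5, 0.8-1.1 and 1.2-1.7 points (at most 5.2%, 5.8% and 7.0%).

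**6. Does the weight help?** A second model used monthly events, overlapping recall windows and ideal weights that include arm, which is kinder than the SAP's. Here completion is per survey, and the 6-month yes rate is 15-37%. Equal 80% completion gave no difference. At 60% vs 85% the false difference was 4.4-6.4 points, with rejection of 11.7-16.6% at 120 per arm and 17.0-23.5% at 185. At those rates 93% and 99.6% of men have at least one survey, so the weights are close to 1 and change little.

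**The case against.** The strongest reply is that the harm is conditional and every size above is assumed. No completion rate by arm appears in the documents. With a 10-point gap in completing all three surveys, type I error stays below 6%, and 1.1 to 1.7 points is small beside the detectable differences of 11.0 to 17.6 points, which the SAP gives for evidence-based care. This stands: the larger error rates are not what one should expect by default.

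The lower end may also be lower than shown. With lasting differences in event rates between men (log-normal SD 1 to 2), 50% vs 80% gives 2.7 to 4.3 points (7.1% to 10.4%). A latent correlation of 0.8 gives 2.7 to 2.9 points. This narrows the size but does not remove the effect.

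SAP section 6 plans single-timepoint and longitudinal comparisons, and for evidence-based care SAP section 4 says "we estimated 80% power at 12-month follow-up to detect minimum between-groups difference". In the second model, a 12-month outcome or a pooled per-survey outcome with wave-specific weights behaved properly (at most 0.3 points; rejection 4.2% to 6.2%). But these answer different questions from the ever/never outcome, and neither is named primary.

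Finally, the missing scoring rule is arguably the firmer defect, and the case for evidence-based care is weak without a recall window. Both are fair, and the fix starts with the scoring rule.

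**Conclusion.** The concern holds in its conditional form. It follows from the documents alone that a man's utilization score depends on how many surveys he completed, and that a weight for any versus no follow-up cannot correct this. Whether bias results depends on completion differing by arm, which is not documented; with equal completion the false difference is zero.

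Under the stated assumptions it is minor at 70% vs 80% completing all three surveys. At 50% vs 80% it is up to about 6 points, with type I error up to about 15% at 120 per arm, if any flagged survey counts. It is smaller and of uncertain sign if absence of a visit is judged over the whole period. I rate this a worthwhile low-cost improvement, with medium confidence in its size.

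**What to change.** Make these changes before analysis:

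- State whether absence of an ambulatory visit is judged per survey or over the whole period.
- Keep the whole-period outcome, but multiply impute missed 4-, 8- and 12-month reports. Include arm, baseline outcome, covariates and observed waves in the model, and impute the utilization components separately. Score the yes/no in each completed data set and pool. State whether men with baseline only are imputed or handled by the existing weight.
- If weighting is preferred, use men with all three surveys, weighted by the inverse probability of observing all three. Per-wave weights do not repair an ever/never outcome: they left errors of 0.8-4.4 points, against 0.9-4.5 with the planned weight.
- Report the number of completed surveys by arm.
- Give the 12-month outcome as a sensitivity analysis, labelled as a different estimand.

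**Cost.** SAP wording and modest programming, with no new data. Imputation assumes missing at random given arm, baseline outcome and observed waves. In runs with 120 per arm, 50% vs 80% completion and rates of 0.3-0.4, it moved the false difference from 4.6-5.9 points to between -0.4 and 0.0, and type I error from 12.7-15.4% to 3.4-4.8%, for a standard error 4-8% larger. Using only men with all three surveys raised the standard error by 21-26%. At a rate of 0.05 the gain is small: -0.8 points after imputation against 1.7 as planned.

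**Limits of these runs.** The trial-size runs used a single outcome, with completion depending on arm alone and every man having at least one survey. Imputation of the composite was checked only in large samples (400,000 per arm) with two independent components; there the error fell from between -1.8 and 3.4 points to within 0.11.

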# 6. Plans for interim and final analysis and statistical analysis of the primary and secondary variables and other data

All analyses detailed above including timepoint specific follow-up as well as overall longitudinal models will compare intervention conditions on change in primary and secondary outcomes.

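### The any-follow-up nonresponse weight does not correct for loss between waves, which exposes the month-8 and month-12 coping comparisons if dropout follows earlier coping differently by arm

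*Combined protocol and SAP*

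**What the plan says.** SAP section 3 states the purpose: "To address potential bias from differential randomization and dropout, we will use covariates and non-response weights". The weight is then defined: "Weights will be created using the inverse of the estimated probability of completing any follow-up survey". The groups it separates are "participants with complete data for at least one follow-up wave versus participants with only baseline data", and its predictors are limited to "socio-demographic and psychosocial variables that were not missing for any participant". A follow-up coping score is missing for every man without that follow-up, so it cannot enter the weight model.

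SAP section 4 analyses coping with a repeated-measures linear regression that has "fixed effects for intervention condition, baseline value of the outcome, and covariates, employing a sandwich estimator to account for within-participant clustering". The same section says of the number of rows per man that "each participant can contribute up to three follow-up responses". No working correlation is stated. SAP section 6 then covers "All analyses detailed above including timepoint specific follow-up as well as overall longitudinal models".

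Section 4 does not mention the weights again; I read section 3 as applying them to the coping models. Neither the protocol nor the SAP gives a wave-specific weight, imputation, a missing-data assumption, a sensitivity analysis or retention by wave.

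**The concern.** The event being weighted does not match the analyses that use the weight. It restores the men who never returned. It does nothing for a man who returned once and then left. At month 12 he has no row, and the men who are there carry weights that treat him as already accounted for. The sandwich estimator corrects the standard error for repeated answers from one man; it does not move the estimate. Adding study arm to the any-follow-up weight does not help, because the modelled event stays the same.

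The arms differ in a way that could affect who stays. Protocol section 2 gives the control arm no treatment, and protocol section 6 offers the other arm eight group sessions on coping. If, for example, intervention men who cope poorly at month 4 tend to leave while control men leave regardless of coping, the month-12 contrast shows a benefit that is not there.

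**Working it through.** **1. Inputs from the documents.** 370 enrolled, about 1:1 (protocol sections 2 and 4); 240 analysable, 120 per arm, and 0.36 SD detectable with 80% power (SAP section 4). Retention by wave and the dropout mechanism are not given, so they are assumed below.

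**2. The plan's own figure.** Two-sided 5% (assumed; not stated): detectable difference = (1.960 + 0.842) × √(2/120) = 0.362 SD, and power at 0.36 SD is 79.6%. The figure reproduces, and this point does not dispute it. It serves only as a yardstick.

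**3. How many men could be involved.** Suppose 240 of 370 (64.9%) are seen at month 12 and 70% to 90% return at least one survey.
- At 90%: 0.90 × 370 = 333; 333 − 240 = 93 men, or 93/333 = 28% of those weighted as responders, lack month 12.
- At 70%: 0.70 × 370 = 259; 259 − 240 = 19 men, or 7%.
- If losses split evenly between months 8 and 12, these men still supply 16% of pooled rows in the first case, (0.125 × 1 + 0.125 × 2)/(0.375 + 3 × 0.65), and 4% in the second, (0.025 × 1 + 0.025 × 2)/(0.075 + 3 × 0.65).

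**4. First-order size of the bias.** Let the chance p of staying for the next wave have a logit slope of s per SD of the last coping score. Among those who stay, the mean of a later score, adjusted for baseline, shifts by about s × (1 − p) × c per step, where c is the between-wave covariance after removing baseline. Take correlation 0.5 with baseline and 0.60 between waves, so c = 0.60 − 0.25 = 0.35; s = 0.7; p about 0.87.
- One step: 0.7 × 0.13 × 0.35 = 0.032 SD. Two steps (to month 12): 0.064 SD.
- Dependence in one arm only: contrast biased by 0.064 SD. Opposite directions: 2 × 0.064 = 0.13 SD. Same in both arms: 0.064 − 0.064 = 0.
- Pooled with independent rows, one arm, retention 0.877/0.765/0.669: (0.765 × 0.032 + 0.669 × 0.064)/2.311 = 0.029 SD.

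**5. Simulation of the same set-up** (1,000,000 men, monotone dropout, any-follow-up weight; true effect 0 and 0.36 SD). Bias in SD:

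| Later dropout depends on | Pooled, independent rows | Month 12 |
|---|---|---|
| nothing | 0.002 | 0.000 |
| baseline coping | 0.002 | 0.001 |
| previous score, same in both arms | −0.002 to 0.002 | −0.010 to 0.002 |
| previous score, one arm | 0.030 | 0.063 |
| previous score, opposite by arm | 0.059 | 0.128 |

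Wave-specific weights using arm, the previous score and their interaction bring every row to 0.002 SD or less.

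**6. Other settings.** With retention 88/75/64% and no true effect, month-12 bias was 0.03 to 0.07 SD (one arm) and 0.07 to 0.12 SD (opposite); the example in step 5 lies at or just above the top because its c is large. An exchangeable correlation of 0.5 gives c = 0.5 − 0.25 = 0.25. With milder loss (92% any survey, about 79% at month 12), bias was 0.02 to 0.04 SD. The formula agrees for one arm: p per step = √(0.79/0.92) = 0.927, so 2 × 0.7 × 0.073 × 0.35 = 0.036 SD, and about 0.07 SD if directions are opposite. A repeated-measures model brought bias to within 0.003 SD.

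**7. Working correlation in the pooled model.** With arm-differential dropout at 88/76/65% retention and random month-4 response, independent rows gave 0.015 to 0.046 SD; a correctly specified exchangeable working correlation gave 0.000 to 0.002 SD.

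**8. Against the yardstick.** 0.03/0.36 = 8% and 0.12/0.36 = 33%; for milder loss 0.02/0.36 = 6% and 0.04/0.36 = 11%.

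**The case against.** Several stronger readings are tempting, and the documents do not support them.

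- *Early leavers are missing from the coping analysis.* Not so. The section 4 model keeps all their answers ("each participant can contribute up to three follow-up responses (from the 4-, 8-, or 12-month surveys"), so they supply one or two rows. They are absent only from the single-timepoint comparisons after they leave, and the month-4 comparison is untouched by later loss.
- *Bias from dropout remains whatever happens.* Not so. Baseline coping is in the model, and coping-related loss that is equal in both arms cancels. Bias needs an arm-by-coping interaction in dropout. No section offers evidence of one, still less of the opposite-direction pattern behind the largest figures.
- *The main pooled coping result is biased.* That depends on treating rows as independent, a choice the SAP leaves open.
- *The SAP expects 65% at month 12.* It labels 240 a deliberately cautious number for power and gives no retention forecast by wave.

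Coping is also a secondary outcome. How the yes/no primary outcomes are scored for a man who misses a wave is a separate question, not settled here.

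All of this limits the size and reach of the point. It does not remove the mismatch: the SAP names dropout as what its covariates and weights are for, and the weight it specifies covers only one part of it.

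**Conclusion.** The point holds in a conditional form. The weight addresses any follow-up versus none, and nothing in the plan addresses loss between waves that depends on earlier follow-up coping. The exposed analyses are the month-8 and month-12 coping comparisons and, to a lesser degree, the pooled coping model.

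Under assumed 88/75/64% retention and arm-differential dropout of 0.5 to 1.0 logit per SD, month-12 bias is about 0.03 to 0.12 SD (0.13 in the opposite-direction example), or roughly a tenth to a third of the stated detectable difference. Milder loss brings it to about 0.02 to 0.04 SD with dependence in one arm. Pooled bias is about 0.02 to 0.05 SD with independent rows and about zero with a correct exchangeable correlation. Retention, correlations and the dropout mechanism are all assumptions, so these figures show what could happen, not what did. The change is worth making because it is cheap and the data can show whether loss differs by arm.

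**What to change.** Preferred: analyse coping with a likelihood-based repeated-measures mixed model over months 4, 8 and 12, with baseline coping, arm, wave and arm-by-wave, and take the month-4, month-8 and month-12 contrasts from that one model. It uses each man's earlier answers, copes with skipped waves, and is valid if missingness depends only on observed data. State the within-man covariance structure.

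Alternative: keep the marginal regression but weight each wave's record by the inverse probability of completing that wave, built up wave by wave from arm, baseline coping, the latest observed coping score and the arm-by-score interaction. State a rule for a man who skips a wave and returns, since the checks above assumed that nobody does.

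In either case, keep the any-follow-up weight only for analyses with one value per man, and report retention by wave and arm. Fix the choice before coping is compared between arms.

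Cost: a few sentences in SAP sections 3, 4 and 6 and slightly more modelling. For the weights there is a small loss of precision: the SD of the estimate was 0.102 to 0.110 against 0.102 to 0.106, which at the upper ends is (0.110/0.106)² = 1.08, about 8% more variance. Neither option corrects for dropout that depends on coping that was never observed.
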